1.1 Specific Aims

This study aims to test methods of increasing adoption and integration of blood glucose monitoring into electronic medical records, and to measure the impact of widespread adoption on health status of patients with diabetes. To investigate determinants of adoption, the research will combine and test doctor and patient focused approaches to encouraging patient use of blood glucose flow sheets through the online patient portal, MyChart. Adoption will be measured on both the extensive and intensive margin: the number of patients who enter data into the flowsheets at all during the study period, and the mean number of entries per patient during the study period. Conditional on statistically significant increases in adoption, the study will examine corresponding intent-to-treat effects on patient health, and consider possible mechanisms through which health indicators improve or do not improve.

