This research will address two key questions related to integration of blood glucose tracking data into EHRs in a large health system. First, effective use of this new technology requires doctors and patients to update the production process, which may be stalled by inertia or lack of knowledge about the new feature. This study will examine methods for encouraging adoption of the new technology. Additionally, it is not known how systematic, widespread use of blood glucose data by providers through an EHR will impact patient health. These questions will be addressed using a clustered randomized design to test patient and provider focused interventions which encourage uptake of blood glucose tracking through the EHR. This encouragement design will also allow for testing effects on patient health, as measured by A1c test results.

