2.2 Setting/Location

Research will be conducted through the MyChart electronic medical records system with patients of Inova Health Systems primary care offices (27 locations). Half of the 27 primary care offices will be randomly selected to receive treatment, but outcome data (existing electronic medical records data) will be analyzed for the entire study population.

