3.1.1 PRACTICE LEVEL PROMOTION

Providers in the randomly selected group of treatment primary care practices will be encouraged to batch order blood glucose flowsheets for all patients with diabetes with active MyChart accounts. The research team will contact physicians and practice managers with an explanation of the initiative and instructions for completing batch orders and viewing entries through the system. The practice will be advised to complete filling orders over a two week administration period, after which the implementation period will begin. A batch order will trigger two forms of alerts sent to providers, according to the default settings for electronic glucose flowsheets:

1. A bi-weekly report received of values that the patient has entered, or a notification that the patient has not entered data during the interval.
2. A notification when patient entered values are out of range (the patient also gets a notification that their doctor will see this value) according to the following current settings:

Notification Setting	Current Default
Pre-Meal Range (entry outside range=alert)	60-180 mg/dl
Post-Meal Range	100-240 mg/dl
Nighttime Range	60-300 mg/dl

Patients will automatically be notified when the flowsheet has been ordered for them. Additionally, providers will be given text for a secure smart-text message to send to all patients receiving the flowsheets, instructing them to enter data for the study period. The secure message will also provide them with information on how to enter data, and on the benefits of tracking blood glucose. Draft text of this message is included below:

Dear [Patient],

You may have seen that there is a new electronic form available for you to enter your blood glucose results in the MyChart portal. Keeping track of your blood glucose can help you manage your diabetes and reduce your chances for developing complications like heart disease, kidney damage and eye damage. As part of a new Inova program to help patients with diabetes get healthy, I would like you to try entering the results of your home blood glucose tests on MyChart for the next 3 months, through [Date]. Please let me know if you have any questions.

Sincerely,

[Practitioner]

WHAT TO DO NEXT

1. **Get help:** If you need help learning how to measure your blood glucose or getting testing supplies, you can contact [Practice Contact].

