3.4 Endpoints/Outcomes Measurements

Hypothesis: Interfacing with primary care practices to encourage physicians to implement default online orders of blood glucose flowsheets and informational messaging for all patients with diabetes will increase patient adoption.

Outcome Measures: Comparison of individuals between treatment and control practices-- (a) fraction of patients entering blood glucose measurements into MyChart flowsheets during implementation period & follow-up period (dichotomous), (b) mean number of flowsheet entries during implementation period and follow-up period (c) fraction of patients for whom order is placed by doctor

Hypothesis: Additional reminder messaging to patients that (1) emphasizes the value of tracking blood glucose data to the patient OR (2) emphasize the value of tracking blood glucose data to the doctor OR (3) informs patient of their selection for a chance to receive an award conditional on tracking will increase adoption relative to no reminder messaging.

Outcome Measure: Comparison of individuals across reminder messaging assignment groups (within treatment practices)-- (a) fraction of patients entering blood glucose measurements into MyChart flowsheets during implementation period & follow-up period (dichotomous), (b) mean number of flowsheet entries during implementation period and follow-up period

Hypothesis: Promotion of adoption of electronic blood glucose tracking through the means described above will result in the following intent-to-treat effects:

(a) reduction in patient A1c

Outcome Measures: Intent to treat comparison of individuals between treatment and control practices of the following measures at the end of the intervention period and follow-up period: (1) Mean A1c (2) Quartiles of A1c using quantile regression analysis (3) fraction of patients experiencing improvement [reduction] in A1c from baseline (dichotomous) (4) fraction of patients below benchmark 7.0% A1c (dichotomous)

(b) increase in frequency of doctor-patient interaction

Outcome Measures: Intent to treat comparison of individuals between treatment and control practices of the following measures during the intervention period and follow-up period: (1) number of securing messaging (2) number of phone interactions, and (3) number of in-office appointments

(c) changes to treatment plan path

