3.5 Consent

A waiver of informed consent and waiver of HIPAA authorization is requested. The study is an encouragement design aiming to increase uptake of an existing service (electronic flowsheets) provided through Inova's MyChart electronic medical record system, and will not change standards of care. Patients and providers in both the treatment and control groups will have access to electronic flowsheets throughout the study unchanged from baseline. The research presents no more than minimal risk of harm to participants and involves no procedures for which written consent is normally required outside of the research context. Research could not practically be conducted without a waiver of consent and HIPAA authorization due to the number of subjects, online nature of the experiment, and design of the study which will seek to examine outcomes for the identified population regardless of actual use of electronic flowsheets. Outcomes of the research could not practically be studied without access to and use of protected health information. See sections on Data Storage, Risks and Confidentiality for more details.

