4.2 Method of Data Analysis

All data analyzed in this study will be administrative health and use data that is collected as part of routine medical care and record keeping. EPIC has offered to build the SQL queries required to produce the outcome datasets described in this protocol. Outcomes listed in Section 3.4. will be analyzed using regression analysis, including (a) a version with no covariates, (b) a version controlling for patient age/gender, race/ethnicity, A1c at baseline, days since most recent office visit at baseline, and doctor fixed effects. A flag identifying patients who are eventual participants of "Impact of Innovative Interventions on Diabetic Adherence with Digital Sensors" (a study recently submitted to the IRB that may have limited overlap with this population) will also be included in the controls. For outcomes indicating analysis of practice level treatment and control groups, standard errors will be clustered at the practice level.

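### Section 1.1 makes the health analyses conditional on a significant rise in adoption, Sections 3.4 and 4.2 do not, and the condition is never defined

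*Combined protocol and SAP*

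**What the plan says.** Section 1.1 sets the condition: "Conditional on statistically significant increases in adoption, the study will examine corresponding intent-to-treat effects on patient health". The same paragraph defines adoption by patient entries on two margins: "the number of patients who enter data into the flowsheets at all during the study period, and the mean number of entries per patient".

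No other section repeats the condition, and several read as if it did not exist:

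- Section 3.4(a) specifies the A1c outcomes as "Intent to treat comparison of individuals between treatment and control practices of the following measures at the end of the intervention period and follow-up period". Contact (b) and treatment change (c) are listed in the same unconditional way.
- Section 4.2 says that the Section 3.4 outcomes "will be analyzed using regression analysis, including (a) a version with no covariates".
- Section 2.2 says that "outcome data (existing electronic medical records data) will be analyzed for the entire study population".
- Section 3.5, in support of the consent waiver, describes a design that will "examine outcomes for the identified population regardless of actual use of electronic flowsheets".
- Section 1.3 presents the health question as part of the design: "This encouragement design will also allow for testing effects on patient health, as measured by A1c test results".

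Section 3.1.1 describes parts of the practice intervention that need no entry by the patient. One is the provider alert that follows an order: "A bi-weekly report received of values that the patient has entered, or a notification that the patient has not entered data during the interval". Another is a message for providers to send, which explains the benefits of tracking and offers help with measuring glucose and obtaining supplies.

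**The concern.** The randomised comparison of practices on A1c is valid whether or not adoption moves. It estimates the effect of the encouragement, and its data are routine records collected in any case. A condition on adoption adds nothing to that validity. If Section 1.1 were followed literally, a valid A1c result, including a null or a harmful one, could go unreported because a different test missed significance.

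The condition is also loose enough to be settled after the fact. It could refer to any entry or to mean entries (Section 1.1), and to the practice comparison or the reminder comparison (Section 3.4). Section 3.4 adds a third practice-level measure, orders placed, and Section 4.1 labels its minimum detectable adoption effect as flowsheet orders rather than entries. No alpha is given. These tests need not agree, so the choice among them could decide whether the health results appear.

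Entry counts are, moreover, an imperfect proxy for exposure. Once an order exists, the non-entry notice, the message and the help with testing could plausibly alter contact, treatment or testing outside the portal with few MyChart entries.

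**Working it through.** **Which sections carry the condition**

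| Section | Health outcomes | Condition on adoption |
|---|---|---|
| 1.1 | Effects on patient health | Yes |
| 2.2 | Outcome data for all patients | None |
| 3.4(a)-(c) | A1c, contact, treatment change | None |
| 3.5 | Outcomes regardless of flowsheet use | None |
| 4.2 | All Section 3.4 outcomes | None |

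**Inputs, from Section 4.1.** 7200 patients in 24 practices, taken as 12 per arm with 300 patients each (3600 per arm). Adoption: control 2%, ICC 0.1. A1c: SD 1.39, ICC 0.07, baseline correlation 0.80. Messaging comparison: 20% adoption with no reminder, 3600 patients. Alpha, sidedness and power are not stated; two-sided 5% and 80% are assumed.

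**Step 1: reproduce the plan's figures.** The t quantiles on 22 df are 2.074 (97.5%) and 0.858 (80%), sum 2.932.

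- Adoption. Design effect = 1 + 299 × 0.1 = 30.9; effective n per arm = 3600/30.9 = 116.5. Solving d = 2.932 × √{[p1(1−p1) + p2(1−p2)] × 30.9/3600} with p1 = 0.02 and p2 = 0.02 + d gives d = 9.45 points. The plan states 9.5.
- A1c. Design effect = 1 + 299 × 0.07 = 21.93. SE = √[2 × 1.39² × (1 − 0.80²) × 21.93/3600] = 0.0921; 2.932 × 0.0921 = 0.270. The plan states 0.27.

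Both figures reproduce, so the assumed alpha and power are consistent with the plan.

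**Step 2: chance that the condition is met**, if it is the practice-level any-entry test. SE(d) = √{[p1(1−p1) + p2(1−p2)] × 30.9/3600}. The probability is the upper tail of a noncentral t on 22 df beyond 2.074, with noncentrality d/SE.

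| True rise | Treated rate | SE | d/SE | Chance met |
|---|---|---|---|---|
| 5 points | 7% | 0.0270 | 1.85 | 43% |
| 9 points | 11% | 0.0318 | 2.83 | 77% |
| 9.45 points | 11.45% | 0.0322 | 2.93 | 80% |
| 18 points | 20% | 0.0393 | 4.58 | 99% |

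The 18-point row is the plan's own 20% no-reminder rate less the 2% control rate. It takes the 20% to apply to all 3600 treated patients, as the Section 4.1 calculation does. The 9-point row shows what happens if only half the patients have orders and the rest stay at 2%: 0.5 × 20% + 0.5 × 2% = 11%.

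**Step 3: sensitivity to the ICC.** At a 5-point rise:

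| ICC | Design effect | Chance met |
|---|---|---|
| 0.1 (the plan's) | 30.9 | 43% |
| 0.05 | 15.95 | 69% |
| 0.03 | 9.97 | 88% |

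**Step 4: bearing on the A1c power.** The 0.27 in Section 4.1 is the 80%-power effect for an A1c test that is always carried out. It makes no allowance for a prior condition.

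**The case against.** The strongest reply is that the condition is one clause in the Aims, while the operative sections (3.4 and 4.2) commit to the A1c analysis without it, and Sections 2.2 and 3.5 lean the same way. This stands. A reader might infer from Section 1.1 that the A1c result will be dropped if adoption is not significant. The documents do not support that as the settled plan; they support only that the plan is inconsistent. The Section 3.5 wording, in turn, can be read simply as patient-level intent to treat, so it does not settle the matter the other way.

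Second, on the plan's own expectation the condition would almost certainly be met (99%). This also stands. A reader might take the 57% chance of missing at a 5-point rise (100 − 43) as the expected loss. The plan never assumes a 5-point rise, the figure depends on the ICC, and it applies to a single test; if several tests could meet the condition, the chance of missing is lower.

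Third, a reader might conclude that the intervention changes A1c without entries. The documents do not show this. Provider notices follow only from an order, the message is supplied for providers to send, and promotion is not mandated. If adoption is low because few orders are placed, these routes mostly do not operate either. The stated rationale runs largely through physicians seeing patient data.

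Fourth, it is tempting to add that the condition distorts the treatment-on-the-treated estimates. Section 3.4 plans those only across reminder groups within treatment practices, and no distortion has been quantified, so that claim is not made here.

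Finally, testing adoption before health effects is a recognisable hierarchical order in an encouragement design. That can justify an ordered test with a named measure and alpha. It does not justify an undefined condition or withholding the estimate.

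**Conclusion.** The point holds as an inconsistency and an undefined rule. Section 1.1 conditions the health analyses on adoption, Sections 3.4 and 4.2 do not, and nothing says which governs after a null adoption result. How much this matters depends on the true rise: under the practice-level any-entry reading, the condition is met about 43% of the time at 5 points, 77% at 9 points and 99% at 18 points. These figures rest on the plan's 2% control rate and ICC of 0.1, equal practices of 300, an assumed two-sided 5% test and a t reference on 22 df. The case for change does not depend on any one of them, because a valid randomised A1c comparison on routine records should be reported either way. The change should be made before outcome data are examined.

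**What to change.** Delete the condition from Section 1.1. State there, and in Section 4.2, that the practice-level intent-to-treat comparisons in Section 3.4(a)-(c) are estimated and reported with confidence intervals whatever the adoption result. Use adoption only to interpret whether an effect can be attributed to flowsheet use, and name the practice-level any-entry comparison as the measure for that purpose.

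If a hierarchical test order is kept for error control, name its measure, comparison and alpha in advance, and still report the health estimates and intervals when the first test fails.

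The cost is a few sentences and no new data. The downside is that A1c will be reported even where an effect through entries is implausible, so the text must keep the effect of encouragement separate from the effect of flowsheet use.

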1.2 Hypotheses

1.2.1 Interfacing with primary care practices to encourage physicians to implement default online orders of blood glucose flowsheets and informational messaging for all patients with diabetes will increase patient adoption (as defined above).

1.2.2. Additional reminder messaging to patients that (1) emphasizes the value of tracking blood glucose data to the patient OR (2) emphasize the value of tracking blood glucose data to the doctor OR (3) informs patient of their selection for a chance to receive an award conditional on tracking will increase adoption relative to no reminder messaging.

1.2.3 Promotion of adoption of electronic blood glucose tracking through the means described above will result in the following intent-to-treat effects:

- (a) reduction in patient A1c
- (b) increases in frequency of doctor-patient interaction
- (c) changes to treatment plan path

1.2.4 Reminder messaging treatments that induce more intensive use of flowsheets will lead patients to experience larger effects as described in 1.2.3.

1.2.5 Entries of blood glucose data will be predictive of A1c on average and will lower over the study period.

1.3 Background and Significance

The percentage of the US population with diagnosed diabetes increased from 4% to over 7% from 1999 to 2014 (CDC 2016), with nearly \$1 in \$5 of health care dollars spent caring for people with diabetes (ADA 2013). There is substantial evidence that improved average blood sugar control (as measured by

A1c levels) is associated with significant decreases in the probability of complications from diabetes (ADA 2016). Commercially insured patients with type II diabetes who lower their A1c, blood pressure and lipid levels, experience significant reductions in total medical costs (Fitch et al 2013). Recent research also suggests that reduction in blood glucose variability is associated with reduced risk of complications and mortality independently of average blood glucose/A1c (Cavalot et al. 2006) (Sorkin et al. 2005).

For patients who are insulin-dependent, self monitoring of blood glucose (SMBG) is a critical aspect of disease management and regulation of blood glucose levels and variability. A landmark randomized controlled trial comparing intensive insulin therapy guided by frequent blood glucose monitoring to conventional insulin treatment. Intensive therapy delayed the onset and slowed the progression of diabetic retinopathy, nephropathy and neuropathy in patients with IDDM (Diabetes Control and Complications Trial Research Group 1993).

However, for non-insulin dependent type 2 diabetics, there has been some debate over the value of self tracking. The ASIA randomized controlled trial of 689 patients over a period of 24 weeks found that patients assigned to perform 6 SMBG measurements per week had a statistically significant 0.3 reduction in A1c (ITT) after 6 months (Guerci et al 2001). However, the DiGem randomized trial found that SMBG without additional training had no effect on A1c after 1 year (Simon et al 2008). A Cochrane meta-analysis of 12 randomized controlled trials evaluating SMBG found a statistically significant mean reductions in A1c of 0.3 for studies with 6 month follow-up (effect sizes in individual studies ranged from .07 to .69), but no statistically significant change in A1c for studies with a 12 month follow up (Malanda et al 2012). However, the review was criticized for including few studies with 12 month follow-up (two, one of which had only 22 subjects). A more recent meta-study was updated to include the latest RCTs, finding a somewhat larger statistically significant reduction in A1c at 6 month follow-up (-.36), and a statistically significant reduction in A1c at 12 month follow-up (-.28) (Zhu et al 2016).

Potential sources of variation in effects of SMBG on A1c for insulin-naive patients across these studies include the characteristics of the patient population, differences in involvement of physicians and training/education provided to patients, as well as heterogeneity in adherence by patients. Much larger effects were found for newly diagnosed patients in comparison to those with a diagnosis greater than 1 year (-0.54 vs -.28 change in A1c). Some of the studies finding no effect of SMBG included mostly patient populations with already well-controlled A1c. Both meta-studies pooled interventions with different levels of guidance and structure to glucose testing.

Two key factors in enhancing the effectiveness of SMBG seem to be patient adherence and physician involvement (Clark 2007). In one study, structured SMBG was compared to enhanced standard care for 483 poorly controlled insulin-naive type 2 diabetics (Polonsky 2011). Analysis revealed much larger effects for patients who adhered to the intervention (-0.5 A1c change). Additionally, patients in both the treatment and control group of this intervention were assigned to quarterly office visits, with structured SMBG patients instructed to bring their readings to consult with their physician. Availability of this data encouraged primary care physicians to treat glycemia earlier, more frequently, and more effectively. Significantly more patients assigned to structured SMBG group received recommendations for a

treatment change as compared with control subjects. These findings highlight the key role that physician engagement with SMBG data plays in its effectiveness.

Nearly all randomized controlled trials of SMBG have had patients monitor their glucose using either pen and paper or store the information on the monitoring device itself to be brought to an office visit for physician viewing. As emphasized above, physicians play an important role in interpreting blood glucose trends, but likely do not have access to this patient generated data between office visits. Though technology to electronically transmit blood glucose readings is available, it is not widely used as a standard practice of care. The TELEDIAB-1 study piloted the Diabeo system (a smartphone coupled to a website) which incorporated automated advice on the insulin doses required; and remote monitoring by teleconsultation. Use of the system improved A1c by 0.9% vs controls in patients with chronic, poorly controlled type 1 diabetes (Charpentier et al 2011). However, there are few examples of integration of such technologies into Electronic Medical Records systems in a manner that would allow for wide-scale use. One study demonstrated the feasibility of automatically sending data from continuous glucose monitors to EMR patient portals for physician viewing, but did not test the impact of this on patient outcomes (Kumar et al 2016). To our knowledge, there is no randomized trial or prior research testing the causal effects of integrating of data from patient self blood glucose monitoring into EMRs on a wide-scale.

Inova patients can track their blood glucose electronically through MyChart, allowing physicians to view their data in real time and be notified if results are out of range. More recently, functionality has been developed to connect Apple's HealthKit to MyChart, such that patients with compatible glucometers can link them to their smartphones, which can in turn be linked to MyChart to automatically transfer glucometer readings to the EHR. This update streamlines the tracking process for patients with compatible devices. Despite these capabilities however, few doctors and patients at Inova use MyChart's blood glucose flowsheets. In order for patients to use the flowsheets, their physician must place an order through the EMR, and this initial step is rarely taken.

Recent research suggests that informational frictions are a key barrier to updating convention across medical practices (Chan 2016). Anecdotal evidence supports that many physicians at Inova are not aware of blood glucose tracking features in MyChart or how to set up tracking. This study will seek to test an intervention to inform physicians of the tracking capabilities, and give guidance for placing bulk glucose flowsheet orders for all patients with diabetes. This aspect of the intervention is intended to remove barriers to physician action, setting a default such that patients have access to the tracking feature.

However, SMBG is most effective when patients track regularly. Many of the studies discussed above show a correlation between adherence and reduction in A1c. This study will also test the effect of reminder messaging on patient use of the flowsheets. One version of messaging will emphasize physician engagement and monitoring of flowsheet entries. Previous research has shown doctor patient communication is predictive of adherence (Friedman et al 2008). Patients may feel more accountability and value to tracking if they anticipate their physicians will be looking at their results. Additionally, as part of this design, some patients will be given a chance to receive a gift card if they fill out the flowsheets, intended to provide compensation for time spent setting up and learning how to use the

tracking features. Past research in other contexts has shown higher adherence to patient driven behaviors when such compensation is provided (Roski et al 2003).

This research will address two key questions related to integration of blood glucose tracking data into EHRs in a large health system. First, effective use of this new technology requires doctors and patients to update the production process, which may be stalled by inertia or lack of knowledge about the new feature. This study will examine methods for encouraging adoption of the new technology. Additionally, it is not known how systematic, widespread use of blood glucose data by providers through an EHR will impact patient health. These questions will be addressed using a clustered randomized design to test patient and provider focused interventions which encourage uptake of blood glucose tracking through the EHR. This encouragement design will also allow for testing effects on patient health, as measured by A1c test results.

